**Table 1. Demographic and clinical characteristics of patients before matching**

Variables*	Graz (n = 83)	Rennes (n = 192)	Genoa (n = 239)	P	SD (Graz vs. Rennes)	SD (Graz vs. Genoa)	SD (cases vs. controls)
Posaconazole prophylaxis	83 (100)	0 (0)	0 (0)	<0.001	Inf.	Inf.	Inf.
Age at ICU admission in years, median (IQR)	65 (58-71)	64 (55-71)	64 (56-71)	0.640	0.122	0.072	0.095
Male sex	56 (68)	125 (65)	178 (75)	0.095	0.064	-0.156	-0.043
Treatment with tocilizumab	2 (2)	6 (3)	56 (23)	<0.001	-0.064	-0.670	-0.454
Systemic steroid treatment	83 (100)	169 (88)	187 (78)	<0.001	0.522	0.751	0.640
Length of ICU stay in days, median (IQR)	18 (13-33)	14 (10-27)	21 (12-42)	<0.001	0.256	-0.164	-0.008

ICU, intensive care unit; IQR, interquartile range; SD, standardized difference in means or proportions divided by standard error; imbalance defined as absolute value greater than 0.20 (small effect size)

\* Expressed as n (%), unless otherwise indicated

**Table 2. Incidence rate and incidence rate ratio of CAPA before matching**

Center	IR	
Graz (posaconazole prophylaxis)	1.69 CAPA/1000 patient-days in ICU	
Rennes (no posaconazole prophylaxis)	4.50 CAPA/1000 patient-days in ICU	
Genoa (no posaconazole prophylaxis)	3.01 CAPA/1000 patient-days in ICU	
Center	IRR (95% CI)*	P*
No prophylaxis (Rennes and Genoa) vs. prophylaxis (Graz, reference)	2.38 (0.87-9.08)	0.0720

CAPA, coronavirus disease 2019 (COVID-19)-associated pulmonary aspergillosis; CI, confidence interval; ICU, intensive care unit; IR, incidence rate, IRR, incidence rate ratio. Calculation of IR were as follows:

$$IR_{Graz} = (4 \text{ CAPA}/2368 \text{ patient-days in ICU}) * 1000 = 1.69 \text{ CAPA}/1000 \text{ patient-days in ICU}$$

$$IR_{Rennes} = (38 \text{ CAPA}/8437 \text{ patient-days in ICU}) * 1000 = 4.50 \text{ CAPA}/1000 \text{ patient-days in ICU}$$

$$IR_{Genoa} = (12 \text{ CAPA}/3989 \text{ patient-days in ICU}) * 1000 = 3.01 \text{ CAPA}/1000 \text{ patient-days in ICU}$$

\* The exact Poisson method was employed for calculating 95% CI. The P-value is from exact mid-P test.

Overall, 4, 38, and 12 cases of CAPA were registered in Graz, Rennes, and Genoa, respectively. The distribution of proven, probable, and possible CAPA in the different centers was as follows: Graz (n = 0 proven, n = 3 probable, n = 1 possible); Rennes (n = 0 proven, n = 19 probable, n = 19 possible); Genoa (n = 0 proven, n = 12 probable, n = 0 possible).

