## Statistical methods

The primary study analysis was aimed at assessing the impact of posaconazole prophylaxis on the risk of coronavirus disease 2019 (COVID-19)-associated pulmonary aspergillosis (CAPA) in critically ill patients with COVID-19 in intensive care unit (ICU). To this aim, incidence rates (IR) of CAPA in the different centers were first calculated with standard methods, and compared between Graz (all patients undergoing posaconazole prophylaxis) and the other two centers (no patients undergoing posaconazole prophylaxis) for descriptive purposes and unadjusted for confounding factors, by means of the mid-P exact test [1]. Then, to minimize the impact of difference in the case-mix of patients between centers on the risk of CAPA, patients from Graz (i.e., undergoing posaconazole prophylaxis) were matched as a case with controls Genoa and controls from Rennes, according to demographic and relevant clinical variables. Before matching, demographic and clinical characteristics of patients in the three different centers were descriptively compared with the standardized difference (SD) of means and the Wilcoxon test for continuous variables, and with the SD of proportions and the chi-squared test for categorical variables. The SD of means/proportions was also reported for the comparison between cases (i.e., patients from Graz) and controls (i.e., patients from Rennes and Genoa).

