### Matching procedure

#### *1:1 matching*

Each patient from Graz (i.e., undergoing posaconazole prophylaxis) was matched as a case with one control from Genoa and one control from Rennes (i.e., not undergoing posaconazole prophylaxis), employing two separate 1:1 propensity score (PS) matching procedures (one for identifying the control from Genoa and one for identifying the control from Rennes) [2,3]. The following variables were considered for matching cases with controls: (i) age; (ii) sex; (iii) treatment with tocilizumab; (iv) time at risk. We did not match for systemic steroid treatment since all patients from Graz received systemic steroids, thus we consider for possible match only those controls receiving systemic steroids in Genoa and Rennes (i.e., the majority of patients in the two centers). Time at risk was defined as follows: (i) for cases: days on posaconazole prophylaxis plus, if present, days in intensive care unit before posaconazole prophylaxis initiation; (ii) for controls: days in intensive care unit. In order to guarantee equal time at risk in cases and respective controls, we started by matching the case with the longest time at risk (53 days) to possible controls with time at risk equal or longer than 53 days. Then, we selected the case with the second longest time at risk and possible remaining controls with equal or longer time at risk. The procedure was repeated until all cases were matched to one control from Genoa and one control from Rennes. Eventually, for the study analyses, we considered only the period of time at risk in controls (starting from intensive care unit admission) that was equal to the time at risk in the respective case (in order to have an exactly equal time at risk in cases and their respective controls).

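### Table 2 divides CAPA cases by patient-days in ICU with no stated stop at CAPA diagnosis; read as written, every incidence rate is somewhat too low, with a modest effect on the rate ratio

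*SAP*

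**What the plan says.** SAP, Statistical methods, gives no person-time rule: "incidence rates (IR) of CAPA in the different centers were first calculated with standard methods". It describes the comparison between Graz and the other two centres as descriptive and unadjusted.

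SAP Table 2 prints the calculation for each centre. The numerators are case counts: "Overall, 4, 38, and 12 cases of CAPA were registered in Graz, Rennes, and Genoa, respectively". The denominators are patient-days in ICU: 2368 in Graz, 8437 in Rennes and 3989 in Genoa. The resulting rates per 1000 are 1.69, 4.50 ("4.50 CAPA/1000 patient-days in ICU") and 3.01. The pooled ratio, no prophylaxis against prophylaxis, is 2.38 with exact 95% CI 0.87 to 9.08 and mid-P 0.0720.

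The only definition of time at risk is in the 1:1 matching section and serves the matched analysis. It has no stop at CAPA either; the rule reads "for controls: days in intensive care unit".

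**The concern.** An incidence rate for a first event needs person-time during which that event can still occur. Once a patient has CAPA, later ICU days cannot produce a first CAPA. Counting them enlarges the denominator without any chance of adding to the numerator, so the rate is too low. The control centres have 50 CAPA cases and Graz has 4, so the surplus days need not be in proportion across the two arms, and the rate ratio can shift as well.

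Table 2 is the only incidence-rate analysis in the SAP and the only place with a single pooled estimate of no prophylaxis against prophylaxis. Tables 5 and 6 give separate odds ratios for Rennes and Genoa. A descriptive rate still needs a denominator that is correct, or at least declared.

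**Working it through.** **Inputs.** Events and patient-days are from SAP Table 2; ICU stays and patient numbers from Table 1; Graz time at risk from Table 3 (median 15, IQR 10-23) and the 1:1 matching section (maximum 53 days). Mean post-CAPA ICU stay, x, is not in the documents. It is an assumption, shown over a range.

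**1. Reproduce the printed figures.** Rates: 4/2368 = 1.69, 38/8437 = 4.50 and 12/3989 = 3.01 per 1000. Pooled controls: 38 + 12 = 50 events in 8437 + 3989 = 12426 days. IRR = (50/12426)/(4/2368) = 2.382. The exact conditional 95% CI is 0.874-9.082 and mid-P is 0.0720. All agree with Table 2.

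**2. Which days are in the denominator?** If Graz had been counted on the SAP's matching time at risk, with a quarter of patients at the top of each quartile band, the total could be at most about 83/4 × (10 + 15 + 23 + 53) = 2,096 days. Table 2 uses 2368. So Graz was not counted on that definition, and whole ICU stay, as labelled, is the natural reading.

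**3. Remove post-CAPA days, same x in every centre.** The denominators become 12426 − 50x and 2368 − 4x.

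| x (days, assumed) | Control days | Graz days | IRR | Exact 95% CI | mid-P |
|---|---|---|---|---|---|
| 0 (as printed) | 12426 | 2368 | 2.38 | 0.87-9.08 | 0.072 |
| 5 | 12176 | 2348 | 2.41 | 0.88-9.19 | 0.068 |
| 10 | 11926 | 2328 | 2.44 | 0.90-9.30 | 0.063 |
| 20 | 11426 | 2288 | 2.50 | 0.92-9.54 | 0.055 |
| 30 | 10926 | 2248 | 2.57 | 0.94-9.81 | 0.047 |
| 40 | 10426 | 2208 | 2.65 | 0.97-10.09 | 0.039 |

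Mid-P first falls below 0.05 at x = 26. The exact CI includes 1 in every row.

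**4. Allow x to differ.** The corrected IRR is 2.382 × (1 − 4·x_Graz/2368)/(1 − 50·x_control/12426). It exceeds 2.382 only if x_Graz/x_control is below (50/12426)/(4/2368) = 2.38. With 10 days in controls and 30 in Graz, the IRR is (50/11926)/(4/2248) = 2.36 with mid-P 0.076, a move the other way.

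**5. Check the denominators against Table 1.** Mean days per patient are 2368/83 = 28.5 (Graz), 8437/192 = 43.9 (Rennes) and 3989/239 = 16.7 (Genoa).
- Rennes: a mean of 43.9 sits oddly with a median of 14 and an upper quartile of 27.
- Genoa: quartiles 12/21/42 imply at least about 239/4 × (12 + 21 + 42) = 4,481 days, more than the 3989 printed.
- Exchanged: Rennes 3989/192 = 20.8 and Genoa 8437/239 = 35.3, both plausible. The rates would then be 38/3989 = 9.53 and 12/8437 = 1.42 per 1000. The pooled 50/12426, and so the IRR of 2.38, would not change.

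**The case against.** The strongest reply is that no sentence says post-CAPA days were counted. The label and the phrase about standard methods leave room for person-time that was in fact stopped at diagnosis. That stands: inclusion is inferred from the printed label and the absence of any stopping rule. The matching definition is weak support, because step 2 shows that Table 2 does not use it for Graz. What remains is that the formulas are printed in full and the rule is absent.

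A reader might infer that the printed ratio is certainly biased towards 1. The documents do not support this. The direction depends on relative post-CAPA stay, and the Graz mean would rest on four patients.

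A reader might also infer that the correction would make the comparison significant. That needs about 26 or more post-CAPA days on average in every centre, longer than the median whole ICU stay in each (18, 14 and 21 days). Even then only mid-P crosses 0.05. The comparison is labelled descriptive, and the matched logistic regression does not use these denominators.

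Finally, a reader might want corrected rates for each centre. These cannot be given with confidence while the Rennes and Genoa denominators conflict with Table 1.

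**Conclusion.** The point holds as a denominator problem of modest size. If Table 2 was computed as labelled, all three rates are too low as first-event rates, whatever the post-CAPA stay. With equal mean post-CAPA stay of 5 to 30 days, which is an assumption, the IRR rises by 0.03 to 0.19, mid-P moves to between 0.068 and 0.047, and the exact CI keeps 1 inside it. Unequal stay can reduce or reverse the shift. The conclusion rests on reading the label literally and on one CAPA case per patient.

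The apparent mismatch of the Rennes and Genoa patient-days with Table 1 matters more for the centre rates than the post-CAPA days do. An interchange is an inference that only the source data can settle.

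**What to change.** First, check the 8437 and 3989 patient-days against source and reconcile them with the Table 1 ICU stays. Then, in all three centres, end each patient's person-time at the earliest of first CAPA, ICU discharge or death. Recompute the three rates, the IRR, its exact CI and mid-P, label the denominator as patient-days at risk, and state the rule in Statistical methods. If person-time was already stopped at CAPA, stating the rule and correcting the label is enough. How Graz days after the end of prophylaxis are handled is a separate question and should not be folded into this correction.

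The cost is small. The landmark analysis already needs CAPA timing, but only for the matched cohort. Table 5 counts 4 + 17 + 2 = 23 cases there, against 54 in Table 2, so CAPA dates may have to be retrieved for up to 31 further patients.

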**Table 3. Demographic and clinical characteristics of patients after 1:1 matching**

Variables*	Graz (n = 83)	Rennes (n = 83)	Genoa (n = 83)	P	SD (Graz vs. Rennes)	SD (Graz vs. Genoa)
Posaconazole prophylaxis	83 (100)	0 (0)	0 (0)	<0.001	Inf.	Inf.
Age at ICU admission in years, median (IQR)**	65 (58-71)	65 (57-72)	66 (61-71)	0.949	0.016	-0.122
Male sex**	56 (68)	55 (66)	54 (65)	0.946	0.043	0.064
EORTC/MSGERC risk factor present at ICU admission***	8 (10)	5 (6)	5 (6)	0.591	0.148	0.148
ECMO	13 (16)	3 (4)	2 (2)	0.001	0.408	0.504
Treatment with tocilizumab**	2 (2)	3 (4)	1 (1)	0.599	-0.117	0.082
Systemic steroid treatment	83 (100)	83 (100)	83 (100)	-	0	0
Time at risk in days, median (IQR)**	15 (10-23)	15 (10-23)	15 (10-23)	-	0	0

ECMO, extracorporeal membrane oxygenation; EORTC, European Organization for Research and Treatment of Cancer; ICU, intensive care unit; IQR, interquartile range; MSGERC, Mycoses Study Group Education and Research Consortium; SD, standardized difference in means or proportions divided by standard error; imbalance defined as absolute value greater than 0.20 (small effect size)

\* Expressed as n (%), unless otherwise indicated

\*\* Matching variables (for details and definition of time at risk, see methods)

\*\*\* Presence of missing values (0/83 for Graz, 1/83 for Rennes, 0/83 for Genoa)

**Table 4 (sensitivity analysis). Demographic and clinical characteristics of patients after 1:1:1 matching**

Variables*	Graz (n = 83)	Rennes (n = 83)	Genoa (n = 83)	P	SD (cases vs. controls)
Posaconazole prophylaxis	83 (100)	0 (0)	0 (0)	<0.001	Inf.
Age at ICU admission in years, median (IQR)**	65 (58-71)	65 (58-72)	65 (58-71)	0.988	-0.041
Male sex**	56 (68)	59 (71)	53 (64)	0.610	0
EORTC/MSGERC risk factor present at ICU admission***	8 (10)	4 (5)	7 (8)	0.490	0.108
ECMO	13 (16)	4 (5)	2 (2)	0.003	0.408
Treatment with tocilizumab**	2 (2)	2 (2)	1 (1)	0.815	0.042
Systemic steroid treatment	83 (100)	83 (100)	83 (100)	-	0
Time at risk in days, median (IQR)**	15 (10-23)	15 (10-23)	15 (10-23)	-	0

ECMO, extracorporeal membrane oxygenation; EORTC, European Organization for Research and Treatment of Cancer; ICU, intensive care unit; IQR, interquartile range; MSGERC, Mycoses Study Group Education and Research Consortium; SD, standardized difference in means or proportions divided by standard error; imbalance defined as absolute value greater than 0.20 (small effect size)

\* Expressed as n (%), unless otherwise indicated

\*\* Matching variables (for details and definition of time at risk, see methods)

\*\*\* Presence of missing values (0/83 for Graz, 1/83 for Rennes, 0/83 for Genoa)

**Table 5. Multivariable logistic regression of factors associated with development of CAPA after 1:1 matching**

Variables	OR (95% CI)	P
EORTC/MSGERC risk factor present at ICU admission	4.35 (1.15-16.49)	0.031
ECMO	1.85 (0.34-9.99)	0.475
Center		0.007
Rennes (vs. Graz as reference)	6.07 (1.76-20.91)	0.004
Genoa (vs. Graz as reference)	0.59 (0.10-3.53)	0.566

CI, confidence interval; CAPA, coronavirus disease 2019 (COVID-19)-associated pulmonary aspergillosis; ECMO, extracorporeal membrane oxygenation; EORTC, European Organization for Research and Treatment of Cancer; ICU, intensive care unit; IQR, interquartile range; MSGERC, Mycoses Study Group Education and Research Consortium; OR, odds ratio.

Overall, 4, 17, and 2 cases of CAPA were registered in Graz, Rennes, and Genoa, respectively, after 1:1 matching. The distribution of proven, probable, and possible CAPA in the different centers was as follows: Graz (n = 0 proven, n = 3 probable, n = 1 possible); Rennes (n = 0 proven, n = 10 probable, n = 7 possible); Genoa (n = 0 proven, n = 2 probable, n = 0 possible).

[figure not shown]
**Table 6 (sensitivity analysis). Multivariable logistic regression of factors associated with development of CAPA after 1:1:1 matching**

Variables	OR (95% CI)	P
EORTC/MSGERC risk factor present at ICU admission	2.84 (0.70-11.63)	0.146
ECMO	1.48 (0.29-7.50)	0.639
Center		0.002
Rennes (vs. Graz as reference)	5.10 (1.54-16.90)	0.008
Genoa (vs. Graz as reference)	0.80 (0.17-3.80)	0.776

CI, confidence interval; CAPA, coronavirus disease 2019 (COVID-19)-associated pulmonary aspergillosis; ECMO, extracorporeal membrane oxygenation; EORTC, European Organization for Research and Treatment of Cancer; ICU, intensive care unit; IQR, interquartile range; MSGERC, Mycoses Study Group Education and Research Consortium; OR, odds ratio.

[figure not shown]
Overall, 4, 16, and 3 cases of CAPA were registered in Graz, Rennes, and Genoa, respectively, after 1:1:1 matching. The distribution of proven, probable, and possible CAPA in the different centers was as follows: Graz (n = 0 proven, n = 3 probable, n = 1 possible); Rennes (n = 0 proven, n = 9 probable, n = 7 possible); Genoa (n = 0 proven, n = 3 probable, n = 0 possible).

**Figure 1. Flow-chart of the patient selection process**

[figure not shown]
**Figure 1 legend.** Matched cohorts after 1:1 and 1:1:1 matching were both composed of 249 patients, although some different controls could have been selected (for details, see matching methods). COVID-19, coronavirus disease 2019.

**Figure 2. Landmark analysis of 90-day survival in patients with and without CAPA after 1:1 matching**

**Figure 2 legend.** Landmark survival analysis after 1:1 matching, with different time of origin (15, 30, and 45 days in ICU for panel A, B, and C, respectively). CAPA, coronavirus disease 2019 (COVID-19)-associated pulmonary aspergillosis; ICU, intensive care unit.

**Figure 3 (sensitivity analysis). Landmark analysis of 90-day survival in patients with and without CAPA after 1:1:1 matching**

**Figure 3 legend.** Landmark survival analysis after 1:1:1 matching, with different time of origin (15, 30, and 45 days in ICU for panel A, B, and C, respectively). CAPA, coronavirus disease 2019 (COVID-19)-associated pulmonary aspergillosis; ICU, intensive care unit.
